**Revision History**

Date	Author	Rev	Description of Change
19 June 2018	[name]	1.0	Initial revision to submit to WIRB
3 July 2018	[name]	1.1	Revised with comments from [name]
5 July 2018	[name]	1.2	Revised statistical plan to account for positive MRI biopsy only

## **List of Appendices**

### Appendix A    Sponsor Responsibilities

## 1 Purpose

The purpose of this Clinical Investigation Plan and Study Protocol (CIP) is to present information for the *Urology San Antonio MRI/Micro-US Comparison* clinical investigation, including the scientific basis for the study, the procedural details, the ExactVu High Resolution Micro-Ultrasound System (referred to in this document as *ExactVu*), its safety details, and administrative details.

The CIP was developed by Exact Imaging and has been designed in such a way as to optimize the scientific validity and reproducibility of the results of the study in accordance with current clinical knowledge and practice so as to fulfill the objectives of the investigation.

## 2 Scope

This CIP and the investigation itself are designed to meet applicable requirements of FDA for conducting clinical investigations. The contents of the CIP follow the requirements identified in *ISO 14155 Clinical investigation of medical devices for human subjects*.

The investigation is a non-significant risk (NSR) investigation. ExactVu falls under normal FDA parameters.

This plan is also intended to serve as the Investigator's Brochure for the purposes of this investigation. It also serves as the Study Protocol for the purposes of this investigation and provides the procedure details for the biopsy and pathology analysis.

## 3 Definitions

Term	Definition
Adverse Device Effect	
Adverse event related to the use of an investigational medical device
 
NOTE 1 This definition includes adverse events resulting from insufficient or inadequate instructions for use, deployment, implantation, installation, or operation, or any malfunction of the investigational medical device.
 
NOTE 2 This definition includes any event resulting from use error or from intentional misuse of the investigational medical device.

Adverse Event	
Any untoward medical occurrence, unintended disease or injury, or untoward clinical signs (including abnormal laboratory findings) in subjects, users or other persons, whether or not related to the investigational medical device
 
NOTE 1 This definition includes events related to the investigational medical device or the comparator.
 
NOTE 2 This definition includes events related to the procedures involved.
 
NOTE 3 For users or other persons, this definition is restricted to events related to investigational medical devices.

Term	Definition
Case Report Form	Document designed to record all information to be reported to the Sponsor on each subject as required by the CIP
Clinical Investigation Plan and Study Protocol (referred to as "CIP")	
A document that states the rationale, objectives, design, medical procedures and proposed analyses, methodology, conduct and record keeping of the clinical investigation.
 
The Clinical Investigation Plan and Study Protocol is designed in such a way as to optimize the scientific validity and reproducibility of the results of the study in accordance with current clinical knowledge and practice so as to fulfill the objectives of the investigation in determining the safety and performance of a device, including undesirable side effects.

Clinical Investigator's Brochure	
A compilation of the clinical and nonclinical data on the investigational product which is relevant to the study of the investigational product in human subjects.
 
Its purpose is to provide the investigators and others involved in the investigation with the information to facilitate their understanding of the rationale for, and their compliance with key features of the CIP. The Clinical Investigator's Brochure also provides insight to support the clinical management of the study subjects during the course of the clinical investigation.

Clinically significant cancer	
Clinically significant prostate cancer for the purposes of this study is defined as tumors where Gleason score > 6, or ISUP grade > 1.
 
Clinically insignificant cancer is defined as Gleason score = 6 or ISUP = 1.

Comparator	A medical device, therapy (e.g. active control), placebo or no treatment, used in the reference group in a clinical investigation
Declaration of Helsinki	
A statement of ethical principles for medical research involving human subjects, including research on identifiable human material and data. The Declaration of Helsinki was developed by the World Medical Association.
 
The Declaration is intended to be read as a whole and each of its constituent paragraphs should not be applied without consideration of all other relevant paragraphs.

Device Deficiencies	
Inadequacy of a medical device with respect to its identity, quality, durability, reliability, safety or performance
 
NOTE Device deficiencies include malfunctions, use errors, and inadequate labeling.

ROC curve	Receiver operating characteristic curve, a graphical plot used in statistical analysis is created by plotting the true positive rate (TPR) against the false positive rate (FPR)
Study Monitor	
Individual appointed by the sponsor responsible for assessing the investigator's compliance with the CIP and for performing source-data verification.
 
The monitor shall have access to the source documents and other information needed to ensure investigator compliance with the CIP and applicable rules and regulations, and to assess the progress of the clinical investigation.

Term	Definition
	NOTE The monitor is also responsible for reporting to the sponsor on the progress of the clinical investigation, including the compliance of the investigators.
Serious adverse device effect	Adverse device effect that has resulted in any of the consequences characteristic of a serious adverse event
Serious adverse event	
Adverse event that
 
a) led to death
 
b) led to serious deterioration in the health of the subject, that either resulted in
 
 
1) a life-threatening illness or injury
 
2) a permanent impairment of a body structure or a body function
 
3) in-patient or prolonged hospitalization
 
4) medical or surgical intervention to prevent life-threatening illness or injury or permanent impairment to a body structure or a body function
 
 
c) led to fetal distress, fetal death or a congenital abnormality or birth defect
 
NOTE Planned hospitalization for a pre-existing condition, or a procedure required by the CIP, without serious deterioration in health, is not considered a serious adverse event.

Sponsor	Individual or organization who or which takes responsibility for the initiation and/or implementation of a clinical investigation
TRUS	
Transrectal Ultrasound
 
micro-US refers to transrectal ultrasound procedures performed using a high-frequency transducer

Unanticipated serious adverse device effect	
Serious adverse device effect which by its nature, incidence, severity or outcome has not been identified in the current version of the risk analysis report
 
NOTE Anticipated serious adverse device effect (ASADE) is an effect which by its nature, incidence, severity or outcome has been identified in the risk analysis report.

## 5 Clinical Investigation Infrastructure

### 5.1 Responsibilities

All parties involved in the conduct of the clinical investigation shall share the responsibility for its ethical conduct in accordance with their respective roles in the clinical investigation.

The investigation will be conducted in the United States at Urology San Antonio.

Exact Imaging and the principal clinical investigator shall agree to the CIP and any amendments and indicate their approval and agreement by signing and dating the signature page of this CIP.

### 5.2 Contents of the CIP

The CIP includes the information about the topics identified in the following sections. If the required information is written in other documentation related to the investigation, for example consent forms or case report forms, such documentation shall be referenced in this CIP, and controlled according to Exact Imaging's standard operating procedures.

Applicable documents shall be included with this CIP in regulatory submissions as required, and any other referenced documents shall be made available on request to Urology San Antonio or its reviewing research ethics board (Western IRB).

In the event that Exact Imaging decides that any requirement given in sections 5.3 through 5.20 is not applicable, relevant or appropriate, a clear statement justifying the omission of the information specified shall be provided on each occasion.

### 5.3 General information

#### 5.3.1 Identification of the CIP

The title for the clinical investigation is *Urology San Antonio MRI/Micro-US Comparison Study*.

The revision number and date of the document are indicated in the Revision History. The Exact Imaging identifier for the investigation is *EVU-2018-001*.

**Address of the Institution(s)**

***5.3.4 Overview of the investigational protocol***

The investigational protocol describes a study designed to compare ultra-high resolution transrectal micro-ultrasound (micro-US), and multi-parametric MRI (mpMRI). These modalities are both used clinically to identify targets for prostate biopsy, however little data is available to compare their sensitivity. While mpMRI is used clinically to identify targets for biopsy, it is not used for real-time biopsy guidance due to challenges performing the biopsy procedure within the MRI gantry. Instead, targets identified on mpMRI are sampled during transrectal ultrasound guided biopsy as part of the prostate biopsy procedure, often using software assisted fusion products. For this investigation, the biopsy procedure will be guided by transrectal micro-US (current standard of care at Urology San Antonio), and will include systematic (standard, random, extended sextant) plus image-guided prostate biopsies among men with clinical suspicion of prostate cancer and an indication for prostate biopsy. The FusionVu software-assisted fusion feature will be used to sample mpMRI targets.

This investigation furthers two cohort studies which demonstrate similar or superior sensitivity for micro-US over mpMRI from two centers in Europe. This study will provide the first prospective blinded confirmation of these results.

The ExactVu device in particular, and micro-US in general have been studied in a number of other investigations, including a pilot study performed at Johns Hopkins University School of Medicine, in which differences between Ultra High Resolution (UHR) using ExactVu's predecessor (ImagistxProstate) and Low Resolution (LR) transrectal ultrasound in their ability to detect cancerous foci in 25 patients were compared, along with safety and efficacy of this technology. Two other previous studies have been approved through WIRB, including protocol 20131849

which provided the first randomized clinical trial on micro-US and WIRB protocol 20162036 which provided a small initial case series comparison of mpMRI and micro-ultrasound in the active surveillance population. Results from both studies were positive and have recently been presented.

Details about objectives of the investigation are described provided in section 5.7.1. The investigational protocol was developed by Exact Imaging, in consultation with [name] and [name] (Urology San Antonio), and will be followed by the investigative team. Exact Imaging is responsible for the contents of the investigational protocol, and for monitoring the investigation.

## 5.4 Device Description

The ExactVu device is a new commercialized ultra-high resolution ultrasound system. It uses a specialized high-frequency transducer, developed by Exact Imaging Inc, to be used by qualified urologists, radiologists, and trained clinicians for real-time prostate imaging and biopsy procedures. It also supports a customized low-frequency transducer. The platform on which ExactVu operates represents the state of the art in high-resolution micro-ultrasound technology. The ExactVu system first received pre-market clearance from the FDA on December 2nd 2016, and the software version intended for the investigation received pre-market clearance on April 30th 2018 for the following indications for use:

*The ExactVu High Resolution Micro-Ultrasound System is intended for use by qualified medical professionals for diagnostic ultrasound imaging or fluid flow analysis of the human body; the intended uses are: Small Organ (prostate), Transrectal. The system may be used with patients of all ages, but is not designed for pediatric or fetal use.*

The unique features of ExactVu are:

- The ability to scan using high-resolution (micro-US) and conventional transducers (on the same platform without disconnecting either transducer)
- The ability to import and overlay MR data with micro-US images to support image guidance
- Custom keyboard layout tailored to this application
- High-frequency imaging:
  - The ability to leverage high-resolution imaging to target biopsies in the appropriate quadrant(s) at visibly suspicious regions
  - Transducer array and housing designed specifically for prostate imaging
  - Increased image resolution inherent in its design (as compared to conventional ultrasound systems currently available)
  - 21 MHz center frequency (i.e., B-Mode)
  - High performance 512 element transducer
  - RF electronics designed and optimized for ultrasound at high frequency

ExactVu is operated using the keyboard interface, and menu options in the software user interface. The keyboard provides an integrated trackball, which is used to access the menu options. Controls are provided for all typical elements of an ultrasound exam of the prostate, with or without a biopsy procedure, including:

- Management of patient and exam information
- Study types (prostate biopsy)
- Start and stop data acquisition
- Adjust imaging and display settings
- Save images and review previously saved images
- Measure structures and add comments to acquired data
- Display overlays (measurements, annotations, needle guide overlay)

- Print acquired and previously saved images

Onscreen feedback is provided to users to provide information regarding the outcome of user actions, and includes status bar messages and confirmation messages for data edits.

### **5.4.1 Device Identification**

Ultrasound System	ExactVu™ high resolution micro-ultrasound system Serial Number: 6437180005
High-Frequency Transducers (micro-US)	29 MHz High Resolution Transrectal Side-fire Transducers (Linear) Serial Number: 6089170044 Serial Number: 6089170045

### **5.4.2 Purpose of the device in the context of the investigation**

For this investigation, ExactVu will be used to perform the following tasks:

- Using the high-resolution transducer, image the prostate and guide a biopsy needle to physician-selected areas of the prostate
- Using the FusionVu software feature to provide software-assisted fusion of mpMRI images to guide a biopsy needle to physician-selected areas of the prostate
- Store images of the location where biopsy samples were taken
- Provide tools to identify and measure regions of interest

It will be used for procedures with men between 40 and 79 years of age who are scheduled for a prostate biopsy.

### **5.4.3 Materials that contact the patient**

The components of ExactVu that will be in contact with tissues or body fluids include the sterile biopsy needle guide, and the biopsy needle.

During use, the transducer will be covered in a conductive coupling gel and covered by a sterile transducer sheath, and therefore will not be in direct contact with the patient. If the sheath were to be compromised during the procedure, then the transducer, biopsy needle guide and biopsy needle could contact tissues or body fluids.

#### **5.4.3.1 EV29L Transducer construction materials**

The materials used in the construction of the ExactVu transducer are:

- Rexolite by C-LEC Plastics – a polystyrene microwave plastic used for the transducer lens
- Epotek 301 – an epoxy used for gluing the housing sides together, and for gluing the lens to the housing
- PEEK LSG provided by Quadrant – a life sciences grade plastic used to construct the housing

Each material has been tested on its own to meet applicable criteria of ISO 10993-1 – Biological evaluation of medical devices.

The transducer may contact tissues or body fluids only if the sterile transducer sheath is compromised.

#### **5.4.3.2 Biopsy needle guide construction materials**

The biopsy needle guide for use with EV29L is manufactured for Exact Imaging by CIVCO. CIVCO is responsible for the selection of materials for this needle guide and for ensuring that the guide complies with the applicable criteria of ISO 10993 – Biological evaluation of medical devices.

CIVCO is also responsible for completing sterilization and packaging validation.

#### **5.4.3.3 Biopsy needle construction materials**

The biopsy needle will be an off-the-shelf product of gauge size 18, and selected by the investigator who will use it.

#### **5.4.3.4 Qualified Gels**

Exact Imaging follows Health Canada and FDA's recommendations for the use of sterile gels for invasive procedures that pass a device through tissue (i.e., in biopsy procedures).

ExactVu is designed to introduce no increased risk when compared to conventional ultrasound, and as such, Exact Imaging accepts Urology San Antonio may have approved institutional protocols that call for the use of non-sterile gel for transrectal biopsy procedures.

Where non-sterile ultrasound gel is used, investigators must take steps to ensure that the product being used is not contaminated, and the container must be sealed appropriately when not in use. Gels whose packaging indicates that they are to be used for external procedures only must not be used. Where non-sterile ultrasound gel is used, Exact Imaging recommends the use of single-dose gels.

#### **5.4.3.5 Sterile transducer sheath**

Sterile transducer sheaths will be used for imaging procedures. For biopsy procedures using the EV29L transducer, off-the-shelf sterile transducer sheaths will be supplied by Exact Imaging.

#### **5.4.3.6 Transducer reprocessing**

Investigators will be provided with instructions for cleaning the ExactVu system and the high-level disinfection of applicable components. These instructions meet the applicable criteria of FDA guidance documents regarding diagnostic ultrasound marketing/licensing.

The instructions can be found in the document:

- Care, Cleaning and Use Guide for EV29L™ High Resolution Transrectal Side-fire Transducer

#### **5.4.4 Instructions for use**

Instructions for use for ExactVu and its accessories are provided in ExactVu labeling, as identified in section 5.8.4.2.

Information describing the workflow for this clinical investigation can be found in this CIP, which will be provided to investigators.

#### **5.4.5 Training requirements**

ExactVu is intended for use by qualified physicians and radiologists. Its use does not require any additional training in medical procedures or principles of ultrasound technology.

The investigators and applicable Urology San Antonio personnel that will participate in this clinical trial are familiar with the procedures that comprise this protocol, as they have already successfully completed training on the ExactVu platform and have used the high-frequency micro-ultrasound to visualize the prostate and guide prostate biopsy in clinical practice for more than 50 cases. The investigators and personnel at Urology San Antonio are also already familiar with the FusionVu software feature, having used it to sample mpMRI-targets under micro-ultrasound guidance on more than 10 cases.

New training for the purposes of this protocol involves:

- An overview of the case report form, and the case data to be recorded

This training will be documented on the training records that are controlled as per Exact Imaging standard operating procedures.

Each investigator must complete this training before using ExactVu to perform biopsy procedures for this study.

Radiologists reading the mpMRI studies must provide PI-RADS v2 reports, and as such must have received training in the PI-RADS v2 protocol. Evidence of this training is to be provided by Urology San Antonio and their radiology partners.

#### **5.4.6 Medical procedures**

Medical procedures to be performed in the study consist of subject preparation, imaging and prostate biopsy. The procedure will be the same for all subjects.

Prior to consent and biopsy, the subject will have been imaged using mpMRI according to the PI-RADS v2 protocol, per the inclusion criteria and standard of care. The radiologist's report must be completed before the biopsy procedure.

The detailed procedure is as follows:

1. Screening and consent visit
2. Biopsy visit:
  - a. Operator 1 (blinded to mpMRI images and report)
    - i. Administer IV sedation per site standard of care
    - ii. Scan with EV29L micro-ultrasound transducer (ExactVu system)
    - iii. Save sweep of prostate
    - iv. Record any suspicious regions (PRI-MUS 3+)
    - v. Measure prostate volume (optional)
    - vi. Targeted biopsy samples (from micro-ultrasound)
      1. Samples from each targeted lesion will be placed in a separate labeled jar to ensure they can be independently discussed on the pathology report
    - vii. Systematic biopsy samples (fill in up to 12 samples)
  - b. Operator 2 (unblinded to mpMRI images and report)
    - i. Align labeled mpMRI sequences with ultrasound using FusionVu software
    - ii. Save a full sagittal sweep through the prostate with mpMRI guidance active for retrospective evaluation
    - iii. Targeted biopsy samples (using mpMRI guidance)
      1. Samples from each targeted lesion will be placed in a separate labeled jar to ensure they can be independently discussed on the pathology report

c. Remove transducer, use site-specific standard post-biopsy follow-up

The biopsy procedure takes approximately 30 minutes. The subject is not required to come for additional clinic visits in the context of the study.

Biopsy results will be provided to the subject's physician as per standard of care. Further healthcare decisions and follow-up are outside the scope of this study. The subject's participation in the study is completed following the prostate biopsy.

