#### **Secondary (unpowered) Outcomes:**

- Compare lesion size and shape between mpMRI and micro-ultrasound (follow-up with detailed whole-mount pathology when available)
- Compare detailed pathological findings (cribriform structure, density of cancer, subtype of cancer) with imaging findings in both modalities
- Identify percentage of micro-ultrasound lesions (with positive biopsy result) that can be identified retrospectively using mpMRI (requires retrospective re-reading of mpMRI sequences given list of micro-ultrasound targets)
- Identify percentage of mpMRI lesions (with positive biopsy result) that can be identified retrospectively using micro-ultrasound (requires retrospective re-reading of micro-ultrasound sweeps given list of mpMRI targets)

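### The only ultrasound sweep earmarked for re-reading carries mpMRI guidance and follows Operator 1's cores, and both hindsight-visibility percentages are cued and lack negative targets, so they may run high by an amount the plan cannot estimate

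*Combined protocol and SAP*

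**What the plan says.** Section 5.4.6 has two saved ultrasound sweeps.

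- Step 2.a.iii belongs to "Operator 1 (blinded to mpMRI images and report". It reads only "Save sweep of prostate", comes before any core and before the mpMRI is aligned, and has no stated purpose.
- Step 2.b.ii belongs to Operator 2, who knows the mpMRI findings: "Save a full sagittal sweep through the prostate with mpMRI guidance active for retrospective evaluation". It comes after Operator 1's targeted cores (2.a.vi) and after "Systematic biopsy samples (fill in up to 12 samples" (2.a.vii).

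Section 5.7.1 lists two retrospective-visibility outcomes among the secondary, unpowered ones.

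- mpMRI lesions sought on ultrasound: "Identify percentage of mpMRI lesions (with positive biopsy result) that can be identified retrospectively using micro-ultrasound". The method is given as "requires retrospective re-reading of micro-ultrasound sweeps given list of mpMRI targets".
- Ultrasound lesions sought on mpMRI: "Identify percentage of micro-ultrasound lesions (with positive biopsy result) that can be identified retrospectively using mpMRI". The method is given as "requires retrospective re-reading of mpMRI sequences given list of micro-ultrasound targets".

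Section 5.4.6 also places the mpMRI scan before consent and biopsy.

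**The concern.** There are two separate problems.

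The first concerns only the micro-ultrasound re-read. Section 5.7.1 leaves the source sweep open, and the one pointer elsewhere in the plan leads to the less suitable recording. A reader judging whether an mpMRI target can be seen on ultrasound should not have the mpMRI guidance on the image. Nor should the recording follow a set of cores if one from before the cores is available.

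The second concerns both re-reads. The reader is told where to look, and the percentage counts only lesions already shown to be positive. A reader who answered yes every time would score 100%, and nothing planned would reveal it.

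What is at stake is how the two percentages are described. Section 5.5.2.3 already reports, from a nine-subject series, that mpMRI lesions could be seen on micro-ultrasound in hindsight. This trial would restate that finding with up to 120 subjects, and section 5.3.4 presents the study as blinded confirmation of prior sensitivity results. A cued, uncontrolled read does not meet that standard for visibility.

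**Working it through.** The plan attaches no figure, test or margin to these outcomes, so there is no stated number to reproduce. The check has two parts.

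**1. Which image each re-read uses**

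| Item | mpMRI lesions sought on ultrasound | Ultrasound lesions sought on mpMRI |
|---|---|---|
| Images (5.7.1) | Ultrasound sweeps, source not named | mpMRI sequences |
| Candidate recordings (5.4.6) | 2.a.iii: before any core, operator blinded to mpMRI. 2.b.ii: after Operator 1's cores, mpMRI guidance active | mpMRI acquired before biopsy |
| Open to overlay or prior-core effects | Yes, if 2.b.ii is read | No |
| Reader given the other modality's target list | Yes | Yes |
| Lesions counted | Biopsy-positive only | Biopsy-positive only |
| Masking to pathology | Not specified | Not specified |
| Negative targets as control | None described | None described |

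Section 5.8.1.2 on bias deals with the two operators and not with the later re-readers. The case report form content in section 5.8.6 lists no re-read item. The overlay and timing problem therefore belongs to the left column alone, while cueing and positive-only counting belong to both.

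**2. What cueing can do to the percentage**

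Let v be the true share of counted lesions that are visible. Let f be the chance that a reader told the location calls a non-visible lesion visible. The documents give neither, so both are assumptions. The observed share is

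observed = v + (1 − v) × f

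| v | f = 0 | f = 0.1 | f = 0.3 | f = 0.5 |
|---|---|---|---|---|
| 0.30 | 0.30 | 0.37 | 0.51 | 0.65 |
| 0.50 | 0.50 | 0.55 | 0.65 | 0.75 |
| 0.70 | 0.70 | 0.73 | 0.79 | 0.85 |

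For example, 0.50 + 0.50 × 0.3 = 0.65. The inflation is (1 − v) × f, which is zero at f = 0 and largest where true visibility is low: 0.65 − 0.30 = 0.35 in the first row.

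The same observed value can arise from different truths: 0.65 fits v = 0.30 with f = 0.5, and v = 0.50 with f = 0.3. Biopsy-positive lesions alone cannot separate them.

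Negative targets help. If w is the true visible share among biopsy-negative targets and f is the same in both groups, the share called visible there is w + (1 − w) × f, which is at least f. The negative group therefore gives an upper limit on f. Because v = (observed − f)/(1 − f) falls as f rises, it also gives a lower limit on v. Suppose positives read 0.75 and negatives read 0.50: then v is at least (0.75 − 0.50)/(1 − 0.50) = 0.50.

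**The case against.** The strongest reply is that the plan defines these quantities openly. They are retrospective, use a list, and cover confirmed lesions. Visibility of a known cancer at a known site is narrower than unprompted detection, but it is a legitimate thing to report. The outcomes are unpowered and play no part in the pass/fail rule of section 5.9.5. The inflation above is hypothetical, and at f = 0.1 it is only 3 to 7 percentage points. All of this stands and limits the weight of the point. It does not supply a check on over-calling.

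A reader might infer four stronger things that the documents do not support.

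- **That the outcomes cannot measure visibility at all.** They measure a cued, conditional form of it, possibly biased upward.
- **That overlay and prior cores spoil both outcomes.** The mpMRI re-read uses images taken before biopsy.
- **That the overlay sweep will certainly be the one read.** Section 5.7.1 does not say so. The 2.b.ii label is not tied to a named outcome and could serve lesion size and shape, or the location of targets. Nor do the documents say whether the overlay can be removed from the stored sweep, or that prior cores degrade it.
- **That the reader knows the pathology.** The plan is silent. The lists are of targets, not of positive targets, so the restriction might be applied only at analysis.

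**Conclusion.** The point holds in a limited form. For the micro-ultrasound re-read, the plan does not name the sweep, and its only retrospective label sits on the one saved with mpMRI guidance active and after Operator 1's cores. A pre-core sweep by the blinded operator has no assigned role. For both re-reads, cueing, positive-only counting, unspecified masking and the absence of negative targets leave percentages that may be too high by an amount the plan cannot estimate.

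No firm size can be given. Over the assumed grid (v from 0.30 to 0.70, f from 0 to 0.5) the inflation runs from 0 to 35 percentage points. It rests on a single over-calling rate and on no figure from the documents. As planned, the results should be described only as cued visibility among confirmed cancers. The primary endpoint and the sample size of 120 do not depend on this.

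**What to change.** - In sections 5.4.6 and 5.7.1, designate the 2.a.iii sweep for scoring the micro-ultrasound re-read. Use the 2.b.ii sweep only to transfer target location, and record the score before the overlay is shown.
- In both re-reads, present all of the other modality's targets, biopsy-positive and biopsy-negative, in random order with pathology withheld.
- Report the percentage identified in positive targets, in negative targets, and the difference. State beforehand what counts as identified.

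The cost is modest. The sweeps, targets and re-reads already arise under the plan, so no extra imaging or cores are needed. Readers score more targets. mpMRI target locations must be carried over to a sweep saved before alignment, and section 5.4.6 does not say that this sweep is a full sagittal one. Some targets may therefore be impossible to assess on it, and these should be counted and reported.
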